4. STUDY DESIGN

Prospective, international, multicenter, observational study in critically ill invasively ventilated patients during a 28–day period in a convenience sample of hospitals globally.

5. STUDY POPULATION

5.1. Population (base)

We will collect data in critically ill invasively ventilated patients that receive ventilation for at least 24 hours. We expect a minimum of 200 ICUs from 30 countries to participate in this prospective international multicenter observational study. Patients will be screened daily during a 28–day period. A registry of limited demographic data will be compiled on all screened patients. Data regarding fluid administration, vasopressor use, diuretics use, oxygen exchange, and kidney function will be collected daily from the start of invasive ventilation. Collection will be retrospective, for the previous day. Clinical complications will be evaluated on day 90 day after start of invasive ventilation, death or hospital discharge, whichever comes first.

5.2. Inclusion criteria

- admitted to a participating ICU;
- receiving invasive ventilation within 3 days of ICU admission; and
- duration of ventilation > 24 hours;

5.3. Exclusion criteria

- age < 16 years;
- patients transferred under invasive ventilation from another ICU;

5.4. Randomization

Not applicable

5.5. Sample size calculation

No formal sample size calculation is necessary for the primary endpoint. However, for investigating associations of aspects of fluid and vasopressor therapy with mortality using logistic regression and adjusting for a limited set of pre-specified confounders, we estimate to need 150 ‘events’ using the 10 event per variable rule of thumb. As fluid and vasopressor management is particularly important in patients with acute respiratory distress (ARDS), we will need at least 150 events in this subgroup. With an incidence of ARDS of approximately 20% and a mortality rate of 30%, we estimate to need 2500 patients to have 150 events in patients with ARDS (37). Assuming that a participating ICU has 50 unique admissions in 4 weeks on average, of which 25% is invasively ventilated for > 24 hours, we expect to need a minimum of 200 participating ICUs (38-40).

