6.2.1. Inclusion

During a 28–day period, all admitted patients are screened daily by a local investigator. To reduce workload in high-volume ICU’s, local investigators can opt to stop study screening and enrollment after every 20 participants. However, once committed to a 20-participant block, researchers must continue until its completion before reassessing.

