8.2. Plan of analysis

Subjects that are transferred to another ICU in the first three calendar days of ICU admission will be excluded from analysis. Subjects that are transferred to another ICU after the first three calendar days, but before seven days are excluded from analysis of the secondary endpoints. Patients admitted due to pancreatitis, burns, diabetic ketoacidosis, severe rhabdomyolysis and sub-arachnoid bleeding will be analyzed separately and excluded from analysis if less than 30 subjects are included in each category. Subjects diagnosed with sepsis or ARDS during the first three calendar days of ICU admission will be part of a subgroup analysis. Associations with outcomes will be assessed through regression modelling. Time to event variables are analyzed using Cox regression and visualized by Kaplan–Meier plots. For each analysis proposed, a complete statistical analysis plan will be prepared, finalized and made available before starting the analyses. Statistical analyses are conducted using R (www.r-project.org). A *P*–value of less than 0.05 is considered statistically significant.

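### Section 5.5 sizes the study for 150 ARDS deaths with no margin, although the protocol's own analysis exclusions reduce the analysable number below the 2500 patients it counts

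*Protocol*

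**What the plan says.** Protocol section 5.5 needs no formal sample size for the primary endpoint. It sizes the study on a logistic regression for mortality, "using the 10 event per variable rule of thumb", and sets the requirement within ARDS: "we will need at least 150 events in this subgroup". It continues: "With an incidence of ARDS of approximately 20% and a mortality rate of 30" per cent, "we estimate to need 2500 patients to have 150 events in patients with ARDS". Taking 50 admissions per ICU in four weeks, a quarter of them ventilated for more than 24 hours, it concludes: "we expect to need a minimum of 200 participating ICUs". The section mentions no allowance for loss.

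Other sections reduce the number of patients who can enter that model:

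- Section 5.2 requires ventilation to start within three days of ICU admission.
- Section 5.3 excludes patients under 16 and "patients transferred under invasive ventilation from another ICU".
- Section 6.2.1 provides that "local investigators can opt to stop study screening and enrollment after every 20 participants".
- Section 8.2 excludes from analysis patients transferred to another ICU in the first three calendar days. Those transferred later but before seven days leave the secondary endpoints, and section 6.1.2 lists mortality among these.
- Section 8.2 also names five admission diagnoses (pancreatitis, burns, diabetic ketoacidosis, severe rhabdomyolysis, sub-arachnoid bleeding) that "will be analyzed separately and excluded from analysis if less than 30 subjects are included in each category".
- Section 8.2 limits the ARDS subgroup to diagnoses made in the first three calendar days of ICU admission.

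**The concern.** The ARDS mortality model is the only analysis on which the sample size rests. Section 5.5 goes straight from patients ventilated for more than 24 hours to deaths in ARDS, as if every such patient were analysed. The exclusions in section 8.2 act after enrolment and can only lower that count. If the chain has no slack, 200 ICUs is too low as the number needed for 150 analysable deaths. At 10 events per variable, 150 deaths support 15 parameters. With fewer deaths, a model of that size would fall short of the rule the protocol adopts.

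**Working it through.** **Inputs from section 5.5:** at least 150 ARDS deaths; ARDS incidence about 20%; mortality 30%; 50 admissions per ICU; 25% ventilated for more than 24 hours; 10 events per variable.

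**The plan's own figures**

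- Patients: 150 / (0.20 × 0.30) = 2500. Reproduced.
- Eligible patients per ICU: 50 × 0.25 = 12.5. ICUs: 2500 / 12.5 = 200. Reproduced.
- Parameters supported: 150 / 10 = 15.
- Margin: 200 × 12.5 × 0.20 × 0.30 − 150 = 0.

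The 150 is an expected value. With no loss at all, and treating each of 2500 patients as an independent 6% chance (0.20 × 0.30) of being an ARDS death, the exact binomial probability of 150 or more is about 51%. It is about 27% after a 5% loss and 10% after a 10% loss.

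**Analysis exclusions.** No loss rate is given, so d below is an assumption, taken to affect ARDS deaths in the same proportion as patients. Expected deaths at 200 ICUs = 150 × (1 − d). Patients needed to keep 150 = 2500 / (1 − d), rounded up. ICUs needed = that number / 12.5, rounded up.

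| Assumed loss d | Expected ARDS deaths at 200 ICUs | Patients for 150 deaths | ICUs for 150 deaths | Deaths per parameter if 15 are used |
|---|---|---|---|---|
| 2% | 147 | 2552 | 205 | 9.8 |
| 5% | 142.5 | 2632 | 211 | 9.5 |
| 10% | 135 | 2778 | 223 | 9.0 |
| 20% | 120 | 3125 | 250 | 8.0 |

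**Optional stop after 20 participants, taken alone.** Suppose every ICU that reaches 20 stops there. Let X be the eligible count per ICU, with mean 12.5. Expected deaths = 200 × E[min(X, 20)] × 0.06. X is Poisson, or negative binomial with an assumed between-ICU coefficient of variation (CV) of the underlying volume.

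| Assumed variation in ICU volume | Mean enrolled per ICU | Expected ARDS deaths |
|---|---|---|
| Poisson only | 12.46 | 149.6 |
| CV 0.3 | 12.23 | 146.8 |
| CV 0.5 | 11.71 | 140.5 |
| CV 0.75 | 10.81 | 129.7 |
| CV 1.0 | 9.82 | 117.8 |

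The stop therefore costs from under 1 death to about 32. The documents give neither its uptake nor the spread of ICU volumes.

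The two sources of loss should not simply be multiplied. The stop counts participants, so losses before enrolment make it bind less often. With CV 0.5 and a 15% loss, about 119 deaths remain if all the loss follows enrolment (140.5 × 0.85), and about 123 if it all precedes it.

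**The case against.** **Nothing is miscalculated.** This is correct. Both products hold exactly; what is missing is an allowance.

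**A reader might infer that the study will fall short of 150.** The documents do not support that. Sections 5.1 and 5.5 both call 200 ICUs a minimum. Before losses, 210 ICUs give 210 × 12.5 × 0.06 = 157.5 deaths and 220 give 165, so 5% to 10% more ICUs would absorb roughly a 5% to 9% loss. The inputs are also rounded: at 200 ICUs, an ARDS incidence of 21% or 22% gives 157.5 or 165 deaths. What remains is that section 5.5 presents 200 as the number needed, and at the stated rates it is too low for that.

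**A reader might count every eligibility limit as a further loss.** That cannot be established. The 25% and 20% come from cited studies, and the protocol does not say whether those figures already leave out children, ventilated transfers-in or later ARDS. Subtracting them again could double count. The exclusions in section 8.2 that apply to enrolled patients do not share this doubt.

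**The stop after 20 is voluntary** and set above the mean yield of 12.5. It matters only if ICU volumes vary widely and uptake is high, so it is a possible contributor and not the basis of the point.

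**The five diagnoses may cost little.** They are analysed separately and dropped only when small, and their share of ARDS deaths is not given. They still leave the main model.

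**A reader might infer that the 10-per-variable rule will be broken.** The protocol does not commit to 15 parameters; it speaks of a limited set of confounders. The choice and ranking of confounders belong in the analysis plan that section 8.2 promises. Even with 15 parameters, a 5% to 10% loss gives 9.5 to 9.0 deaths per parameter against a rule of thumb.

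**Conclusion.** The point holds in a limited form. Section 5.5 reaches its required ARDS deaths with zero margin, while section 8.2 removes enrolled patients from the mortality analysis that section 5.5 sizes. At exactly 200 ICUs and the stated rates, any non-zero loss puts expected analysable ARDS deaths below 150. The direction follows from the protocol. The size does not, because no loss rate, opt-out uptake or spread of ICU volumes is given. Over assumed losses of 2% to 20%, the shortfall at 200 ICUs runs from 3 to 30 deaths. No single range, such as 120 to 135 deaths, can be presented as what the design will deliver. The consequence is modest: it concerns a subgroup model for a secondary aim and leaves the descriptive primary aim untouched. It deserves correction because this is the only calculation behind the study's size and the correction is cheap.

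**What to change.** Revise section 5.5 in four respects:

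1. State that 2500 patients in 200 ICUs is the analysable number required after losses.
2. State the sponsor's expected loss d, covering the section 8.2 exclusions. Add the eligibility limits to the extent that the cited 25% and 20% do not already reflect them, and the expected use of the stop after 20 participants.
3. Give the resulting expected ARDS deaths at 200 ICUs, 150 × (1 − d). If 150 is to be kept, give the inflated targets instead: 2500 / (1 − d) patients and 200 / (1 − d) ICUs.
4. Limit the ARDS mortality model to observed ARDS deaths in the analysis set divided by 10, counting every estimated coefficient.

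The value of d must come from the sponsor; the figures above only show how the result responds to it. The cost is a few sentences and a slightly less favourable event count. No extra patients are needed unless the sponsor chooses to hold 150, in which case the ICU target rises by the factor 1 / (1 − d). The model may have to be somewhat smaller than 15 parameters.

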6. METHODS

6.1. Study parameters

6.1.1. Primary parameter

- Quantity, timing and type of intravenous fluids administered.

6.1.2. Secondary study parameters

- Time of start of vasopressors;
- Route of administration for vasopressors (i.e. central vs. peripheral route);
- Types of vasopressor used;
- Daily urine output;
- Cumulative fluid balance;
- Timing of start, type and infusion time (i.e. bolus vs. continuous infusion) of administered diuretic;
- Incidence of atrial arrhythmias;
- Incidence of acute respiratory distress syndrome (ARDS)
- Incidence of renal replacement therapy;
- Incidence of persistent renal dysfunction, defined as the need for renal replacement therapy at ICU discharge;
- ICU length of stay, defined as the time between ICU admission and discharge or death;
- Hospital length of stay, defined as the time between hospital admission and discharge or death;
- Duration of ventilation, defined as the time between initiation of invasive ventilation and successful liberation of ventilation.
- Ventilator-free days and alive at day 28, defined as 28 - x if successfully liberated from ventilation x days after initiation. If subject dies within 28 days ventilator-free days is set to 0;
- All-cause ICU mortality, defined as any death during ICU stay;
- All-cause in-hospital mortality at day 28, defined as any death during hospital stay before or on study day 28;
- All-cause in-hospital mortality at day 60, defined as any death during hospital stay before or on study day 60;
- All-cause in-hospital mortality at day 90, defined as any death during hospital stay before or on study day 90;

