6.2. Study procedures

Patients in participating centers are screened on a daily basis. Eligible patients are included during the 28–day observation period, from Monday at 8:00 AM to the Monday four weeks later at 7:59 AM (in time zones of the participating centers). The timing of the 28–day observation period will be flexible for participating centers and determined at a later stage together with the international study–coordinator and each national investigator. Times points of data collection:

- Demographic and baseline data are collected from the clinical files – at ICU admission;
- Types, quantities, of administered fluids– during the first three calendar days with high-granularity. From day 4-7 lower granularity data concerning the total volume of infused fluids will be collected;
- Types and modalities of administration of vasopressors – over a maximum of seven days of ICU admission;
- Vital signs, laboratory results and limited treatment parameters are collected – once daily for a maximum of seven days;
- Cumulative fluid balance – calculated once a day on a time point convenient per each center for a maximum of seven days; and
- Outcomes – recorded at 90 days, the day of death or hospital discharge, whichever comes first.

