- Arterial or venous lactate, mmol/L , at a convenient fixed time point;
- Serum sodium, mmol/l , at a convenient fixed time point;

- Serum chloride, mmol/l, at a convenient fixed time point;
-
- S(c)VO₂, mmol/L, highest and lowest value;
- PaO₂, kPa or mmHg, at a convenient fixed time point;
- (if no PaO₂ is known) Peripheral arterial oxygen saturation (SpO₂), percentage, at a convenient fixed time point;
- Inspired oxygen fraction, %, at time of PaO₂ or (if no PaO₂ is known) SpO₂;
- Was there new-onset (<7 days) respiratory symptoms, or acute worsening of respiratory symptoms?, yes/no, if yes;
- Are there bilateral opacities on chest imaging (including lung ultrasound), yes/no;
- If there was hypoxemia, was the hypoxemia explained by cardiac failure, yes/no?
- Richmond Agitation Sedation Scale (RASS), highest value of the day; and
- SOFA score.

D. Daily on day 3 to 7 or ICU discharge; and on day -1, day -2 and day -3;

- Total volume of infused fluid, ml, over 24 hours
- Cumulative fluid balance, ml, over 24 hours;
- Urine output, ml, over 24 hours;
- Extracorporeal life support, venoarterial/venovenous/no;
- Renal replacement therapy, yes/no, if yes;
 - Volume extracted by ultrafiltration, ml, over 24 hours;
- Loop diuretics given, yes/no, if yes;
 - Furosemide, yes/no, if no;
 - (if no furosemide used) Bumetanide, yes/no, if no;
 - (if no bumetanide or furosemide used) Torasemide, yes/no;
 - (if no Torasemide, bumetanide, furosemide used) Edecrin, yes/no;
 - Additional diuretic given (thiazide, carbonic anhydrase inhibitor or mineralocorticoid antagonist), yes/no;
- Serum creatinine, µmol/L or mg/dL, at a convenient fixed time point;
- Serum hemoglobin, µmol/L or mg/dL, at a convenient fixed time point;
- Serum albumin, at a convenient fixed time point;
- Vasopressors used, yes/no, if yes;
 - Drug(s) used as vasopressor;

- MAP, mmHg, at a convenient fixed time point;
- Heart rate, beats/min, at a convenient fixed time point
- Atrial fibrillation or flutter during the last day, yes/no;
- Arterial or venous lactate, mmol/L, at a convenient fixed time point;
- Serum sodium, mmol/l, at a convenient fixed time point;
- Serum chloride, mmol/l, at a convenient fixed time point;
- PaO₂, kPa or mmHg, at a convenient fixed time point;
- (if no PaO₂ is known)) Peripheral arterial oxygen saturation (SpO₂), percentage, at a convenient fixed time point;
- Inspired oxygen fraction, %, at time of PaO₂ or (if no PaO₂ is known) SpO₂; and
- SOFA score.

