E. Events (at day 7 or ICU discharge, whichever comes first)

- Were vasopressors initiated before ICU admission?, yes/no;
 - If no: Date of initiation of vasopressors after ICU admission, date;
- Route of initiation of vasopressors, central venous/peripheral venous;
- Did the patient develop AKI; yes/no;
 - if yes, on which study day?, day;
- Did the patient develop rhabdomyolysis; yes/no;
 - if yes, on which study day?, day;
- If the patient was admitted for sepsis, what was the suspected or proven pathogen causing the sepsis?

F. Follow-up (at hospital discharge, day 90, or death, whichever comes first)

- Vital status, alive/dead, if dead;
- Date of death;
- Reintubation, yes/no, if yes;
 - Number of reintubations;
 - Date of initial extubation;
 - Date of reintubation;
- Date of last extubation (or in the case of tracheostomy 24 hours without support from the ventilator);
- Date of ICU discharge;

- Date of hospital discharge; and
- Subjects requires renal replacement therapy or hemodialysis, yes/no.

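### Three secondary endpoint definitions need data that the protocol's own collection list does not fully supply: hospital admission date, diuretic mode, and renal replacement therapy at ICU discharge after day 7

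*Protocol*

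**What the plan says.** Protocol section 6.1.2 lists 18 secondary parameters. Three matter here:

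- Hospital stay: "Hospital length of stay, defined as the time between hospital admission and discharge or death".
- Diuretics: "Timing of start, type and infusion time (i.e. bolus vs. continuous infusion) of administered diuretic". The Summary also names diuretic infusion time among the secondary outcomes.
- Kidney: "Incidence of persistent renal dysfunction, defined as the need for renal replacement therapy at ICU discharge".

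Section 6.2.3 presents itself as the list of data collected for every enrolled patient, in blocks A to F. Loop diuretics appear as daily yes/no items by drug, for example "Furosemide, yes/no, if no". RRT is a daily yes/no item in blocks B, C and D, the last of which is headed "D. Daily on day 3 to 7 or ICU discharge; and on day -1, day -2 and day -3". The only RRT item after that reads "Subjects requires renal replacement therapy or hemodialysis, yes/no" and stands under the heading "F. Follow-up (at hospital discharge, day 90, or death, whichever comes first". Section 6.2 gives the same timing: "Outcomes – recorded at 90 days, the day of death or hospital discharge, whichever comes first".

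**The concern.** Each of the three definitions contains an element that must be recorded at the bedside or taken from the chart: a start date, a mode of administration, or a status on a given day. If the element is not on the collection list, a later analysis plan can change the definition but cannot supply the datum.

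The risk is that results are reported under labels they do not meet. Hospital stay would lose the days before ICU admission. The renal proportion would be taken at another time point, or only in patients with short ICU stays. Diuretic mode would drop out without comment. Section 3.1 makes associations between therapy and clinical outcomes an aim, so hospital stay and renal outcome are candidates for modelling as well as description. With at least 200 ICUs in 30 countries expected (section 5.1), going back to charts afterwards would be expensive.

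**Working it through.** There is no stated figure to reproduce. The check sets each definition in 6.1.2 against blocks A to F of 6.2.3 and looks for any item that could fill the gap.

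| Endpoint | Needed | Listed in 6.2.3 | Gap |
|---|---|---|---|
| Hospital stay | Hospital admission date; discharge or death date | Discharge and death dates (F) | Start date, all patients |
| Diuretics | Start, type, mode | Yes/no by drug and day (B, C, D) | Mode |
| Persistent renal dysfunction | RRT need at ICU discharge | Daily RRT to day 7 or ICU discharge (B, C, D); one undated item (F) | ICU stays beyond day 7 |

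**Hospital stay.** The dates listed are ICU admission and start of ventilation (A), start of vasopressors (E), and extubation, reintubation, ICU discharge, hospital discharge and death (F). None is hospital admission. What can be computed is

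(discharge or death − ICU admission) = defined stay − (ICU admission − hospital admission).

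The subtracted term varies between patients and is recorded for none of them.

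**Diuretic mode.** The daily blocks cover days −3 to −1 (3 days, only for patients not yet ventilated at ICU admission), day 0 (1), days 1 and 2 (2) and days 3 to 7 (5): 3 + 1 + 2 + 5 = 11 days.

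- A field for mode exists on 0 of the 11.
- The rate of each separate infusion, medication included, is collected on 2 of the 11 (block C). A continuous diuretic infusion might be recognised there.
- Day 0 has type and volume of each infusion, without rate.
- The other 3 + 5 = 8 days have total infused volume only.

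Calendar day of first use, within this window, and drug type, as finely as the yes/no items allow, can be derived.

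**Persistent renal dysfunction.** Days are numbered from the start of ventilation (day 0).

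- *Out of ICU by day 7:* the last daily RRT entry gives, or closely approximates, status at ICU discharge.
- *In ICU beyond day 7:* daily recording has stopped. Block E is completed at day 7 for these patients and has an acute kidney injury item but no RRT item. The next entry is in block F. It coincides with ICU discharge only if the patient leaves the ICU and the hospital on the same day.

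Let L be the share of ICU survivors who leave after day 7 without a recorded status, and p the proportion on RRT among the rest. The incidence in all ICU survivors then lies between (1 − L) × p and (1 − L) × p + L, an interval of width L. The protocol does not give L, so the size of this gap cannot be stated.

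**The case against.** The strongest reply is that most of the information is there.

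- **Renal, up to day 7.** Daily RRT covers everyone who leaves the ICU by day 7. This stands and limits the renal point to longer stays.
- **Renal, block F.** The heading of block F says when the form is completed, and several of its items look back to earlier events such as first extubation and ICU discharge. The RRT item may be under-specified rather than mistimed. This also stands: the defect is the missing tie to ICU discharge, and the protocol does not show that the question was meant for a different time.
- **Deaths.** A reader might infer that using block F necessarily mixes RRT need with death. It does not, because block F also holds vital status, date of death and ICU discharge date, so patients who died can be separated.
- **Diuretics.** Two of the three components survive, and day 1 and 2 rates give some handle on the third. On day 0 the furosemide item ends with an unfinished conditional, which may point to a sub-item lost from the printed list. That is possible but not shown.
- **Chronic dialysis.** A reader might infer that, since block A has no chronic dialysis item, the RRT incidence is inflated by a definite amount. The protocol does not support this. It does not define incidence as new RRT, and it gives no figure for chronic dialysis. It also collects the lowest creatinine of the past year where available, and RRT on days −3 to −1.
- **The electronic case report form may hold more fields.** It is not shown. Section 6.2.3 is nonetheless the protocol's statement of what is collected, and if the form goes further, the list should be corrected to agree.

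None of this supplies a hospital admission date, a mode field, or RRT status at ICU discharge for longer stays.

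**Conclusion.** The mismatch is real, and its extent differs by endpoint.

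- Hospital length of stay cannot be computed as defined for any patient.
- The diuretic endpoint loses its mode component, with partial inference possible on days 1 and 2 only.
- Persistent renal dysfunction is unrecorded at its defined time for ICU stays beyond day 7, a share the protocol does not give.

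It would be too strong to say that three endpoints cannot be computed at all; only hospital stay comes to that. The conclusion assumes that section 6.2.3 is the complete collection list. All three are secondary endpoints, so the primary parameter and the sample size are untouched. The correction is still worth making, because an analysis plan cannot restore data that were never collected.

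**What to change.** For each endpoint, either add the field or change the definition:

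1. **Hospital stay.** Add *date of hospital admission* to block A, or redefine the endpoint as time from ICU admission to hospital discharge or death.
2. **Diuretics.** Add *bolus / continuous / both* beneath a positive loop diuretic answer in blocks B, C and D, or remove mode from section 6.1.2 and infusion time from the Summary.
3. **Persistent renal dysfunction.** Add *RRT required at ICU discharge, yes/no*, answered for ICU survivors, or move the endpoint to the block F time point and rename it accordingly.

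The added fields come from the chart and involve no change in care: two one-time items and one conditional daily item. The cost is some extra data entry and a minor amendment across sites, including local ethics submission where required and updated translations of the case report form. The redefinitions largely avoid the new data entry. Their price is a hospital stay that omits days before the ICU, no description of diuretic mode, and a renal outcome at a later time point.

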6.2.4. Follow-up

Participants are subject to follow-up until hospital discharge, day 90 or death.

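### The ventilator-free-day formula has no day-28 limit: liberation after day 28 scores below death within 28 days, and patients alive at day 28 but never liberated get no score

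*Protocol*

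**What the plan says.** Section 6.1.2 lists the outcome as "Ventilator-free days and alive at day 28, defined as 28 - x if successfully liberated from ventilation x days after initiation". It adds one special case: "If subject dies within 28 days ventilator-free days is set to 0". Those are the only two scoring rules. The item just above it, from which x takes its meaning, is also open-ended: "Duration of ventilation, defined as the time between initiation of invasive ventilation and successful liberation of ventilation".

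The observation window is longer than the scoring window. Section 6.2 has outcomes "recorded at 90 days, the day of death or hospital discharge, whichever comes first", and section 6.2.4 says "Participants are subject to follow-up until hospital discharge, day 90 or death". Part F of section 6.2.3, headed "Follow-up (at hospital discharge, day 90, or death, whichever comes first", collects the extubation dates, including "Date of last extubation (or in the case of tracheostomy 24 hours without support from the ventilator" on that same horizon.

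**The concern.** A ventilator-free-day score is meant to put death and failure to come off the ventilator within the window together at the bottom of the scale. This definition places only death there. A patient who is alive at day 28 and still ventilated falls under neither rule at that time. If liberated later, the patient meets the condition of the first rule with x above 28. If never liberated, the patient meets no condition.

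Two things are at stake. First, the order of outcomes: section 8.1 names the Mann-Whitney U test for continuous variables, so the relative position of late liberation and death enters the test directly. Second, completeness: patients without a value would drop out of any analysis of the score, and they are by construction among those ventilated longest. Section 3.1 makes associations between fluid and vasopressor therapy and clinical outcomes an aim of the study, so the score is likely to be used.

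**Working it through.** The protocol states no numerical figure for this outcome, so there is nothing to reproduce first. The check is to apply the two rules to each type of patient.

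**Inputs**
- Score = 28 - x, with x the days from start of invasive ventilation to successful liberation (section 6.1.2).
- Score = 0 for death within 28 days (section 6.1.2).
- No stated upper limit on x and no floor on the score, in section 6.1.2 or elsewhere in the protocol.
- Largest x that can be recorded: about 90, for a patient who stays in hospital (sections 6.2, 6.2.3 part F and 6.2.4).

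**The formula as written, and limited to day 28**

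| Patient | As written | Limited to day 28 |
|---|---|---|
| Liberated day 10 | 28 - 10 = 18 | 18 |
| Liberated day 27 | 28 - 27 = 1 | 1 |
| Liberated day 28 | 28 - 28 = 0 | 0 |
| Liberated day 29 | 28 - 29 = -1 | 0 |
| Liberated day 40 | 28 - 40 = -12 | 0 |
| Liberated day 60 | 28 - 60 = -32 | 0 |
| Liberated day 90 (limit of follow-up) | 28 - 90 = -62 | 0 |
| Died within 28 days | 0 | 0 |
| Died on the ventilator on day 35 | no rule applies | 0 |
| Still ventilated at day 90 | no rule applies | 0 |

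**What changes in a rank comparison.** Patients liberated before day 28 have positive scores in both columns, so their order among themselves and above everyone else is the same. The difference lies in the tail. A patient liberated after day 28 is tied with a patient who died within 28 days when the limit is applied, and ranks strictly below that patient as written. In a Mann-Whitney count, each such pair across groups goes from a tie (one half) to a loss for the late-liberated patient (zero). Late-liberated patients are also ordered among themselves instead of being tied.

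**What changes in a mean.** Compared with scoring late liberations as 0, the mean falls by p × (m - 28). Here p is the share of scored patients liberated after day 28, and m is their mean day of liberation. The protocol gives neither, so no figure follows.

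**The case against.** The strongest reply is that the label ties the outcome to day 28, that a count of days inside a 28-day window cannot be negative, and that the protocol nowhere says negative values will be used. Section 8.2 also promises a full analysis plan before each analysis, where a boundary rule could be set. This is a fair reading of the intent. It does not repair the definition: if 28 - x applies only to liberation by day 28, everyone alive and not liberated by then has no assigned value. The text yields either negative scores or missing ones. And since the protocol chose to state the formula itself, it should state it completely.

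The reply is right about scope. Several stronger readings are tempting and are not supported:

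- A reader might infer that x is always the date of last extubation, so that a reintubation after day 28 makes the score negative even for a patient liberated early. Section 6.1.2 defines x by successful liberation, and part F of section 6.2.3 also collects the dates of initial extubation and of reintubation.
- A reader might infer that the form needs repeatable reintubation dates. The listed dates suffice for a single reintubation. A need for more has not been shown, and the burden would fall on at least 200 ICUs.
- A reader might infer that early hospital discharge spoils the score, because being alive at day 28 is then not observed. That follows from follow-up ending at discharge, which also governs the in-hospital mortality outcomes. It is separate from the missing day-28 limit.
- A reader might infer a general bias against settings that ventilate for longer. Any ventilator-free-day score counts long ventilation as unfavourable, including the corrected one. The literal formula adds only the effect in the tail.
- A reader might say that late-liberated patients rank below every death. Only death within 28 days is set to 0.

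**Conclusion.** The definition is wrong as written, and the consequence is minor. Taken literally, every patient liberated after day 28 scores below 0 (-1 at day 29, -12 at day 40) and so below patients who died within 28 days. Patients alive at day 28 who are never liberated have no score. The negative scores rest on reading the formula literally. Under the narrower reading they disappear, but the unscored group then grows to include all who are alive and not liberated by day 28. The defect therefore stands under both readings.

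The size of the effect on any comparison cannot be stated, because the protocol does not give the share of patients ventilated beyond 28 days. The effect is confined to that tail of one of the 18 secondary parameters listed in section 6.1.2. The primary parameter is fluid administration, and the sample size in section 5.5 rests on deaths among patients with ARDS, so neither is touched.

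**What to change.** Amend the item in section 6.1.2 to say that ventilator-free days equal 28 - x only if the patient is liberated on or before day 28, and equal 0 if the patient dies by day 28 or is still on invasive ventilation at day 28. Add that no value is below 0 and that events after day 28 do not change the score.

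The cost is one sentence. The form already lists the dates of start of ventilation, initial and last extubation, reintubation and death, so this needs no new field, no further follow-up and no change to the sample size. Any later analysis plan that uses the score should carry the same wording.
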